TAT	Thrombin-antithrombin
TB	Tuberculosis
TCAE	Terminology Criteria for Adverse Events
Tid	Three times daily
TNF	Tumor Necrosis Factor
ULN	Upper Limit of Normal
UNOS	United Network of Organ Sharing
WHO	World Health Organization
y.o.	Years old

Study Definitions

Full graft function: Islet transplant recipients will be considered to have full islet graft function if they are insulin independent (as defined below).

Graft failure: Islet allograft failure will be defined as absence of insulin production by transplanted islets, as evidenced by c-peptide < 0.3 ng/mL. This will be determined by (1) c-peptide < 0.3 ng/mL on random testing, followed by (2) c-peptide < 0.3 ng/mL at baseline, and at 60 and 90 minutes after MMTT. Participants with graft failure do not need to complete the day 75 metabolic assessments.

Insulin-independent: Islet transplant recipients will be considered insulin-independent with full islet graft function if they are able to titrate off insulin therapy for at least 1 week and all of the following criteria are met:

- One HbA1c level, one fasting serum glucose level, and a Mixed Meal Tolerance Test are documented within the visit window (e.g. 70-80 days at Day 75) and 7 consecutive days of blood sugar and insulin readings are documented within ± 7 days of the visit window (e.g. 63-87 days at Day 75);
- HbA1c $\leq 6.5\%$ or a $\geq 2.5\%$ decrease from baseline (within 91 days prior to transplant);
- Fasting capillary glucose level should not exceed 140 mg/dL more than three times in 7 consecutive days (fasting is defined as 1st blood sugar reading of the day not noted as post-prandial or bedtime);
- Post-prandial serum glucose ≤ 180 mg/dL at 90 minutes during the MMTT;
- Fasting serum glucose level ≤ 126 mg/dL; if the fasting serum glucose level is > 126 mg/dL, it must be confirmed in an additional one out of two measurements;
- At least one MMTT fasting or stimulated c-peptide ≥ 0.5 ng/mL.

Insulin dependent: Islet transplant recipients who do not meet the criteria for insulin independence will be considered insulin-dependent.

Intensive diabetes management: Self-monitoring of glucose values no less than a mean of three times each day averaged over each week and by the administration of three or more insulin injections each day or insulin pump therapy.

Partial graft function: Islet transplant recipients who do not meet criteria for insulin independence, but have either a basal or stimulated c-peptide level ≥ 0.3 ng/mL (0.1 nmol/L).

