A more recent analysis studied AAT treated bone marrow transplant recipients with steroid refractory GVHD, Marcondes et al utilized a modified every other day regimen of AAT (GLASSIA) that achieved stable serum AAT levels in the desired target range⁷². Their regimen consisted of a 90 mg/kg load followed by 60 mg/kg every other day for 8 doses. We have adopted a modified version of this regimen for our trial that contains a total weekly dose in the Grifols trial of 120 mg/kg/wk.

Based on the above findings, we contend that the diverse inflammation targeting properties of AAT may simultaneously impact critical impediments to islet transplantation – alloimmunity, autoimmunity, and innate/inflammation induced early post-transplant islet loss. Given that in addition to the study patients noted above, AAT has been administered safely long term to large numbers of patients as replacement therapy in the setting of AAT deficiency⁷³⁻⁷⁴, and has proven highly safe even in immunosuppressed post-lung transplant patients, in conjunction with the fact that it is readily commercially available, makes the agent an exciting therapy to improve islet transplant success.

In the current trial, we will capitalize on data from the CIT-06 trial (with permission of the CIT steering committee) that has completed enrollment of 24 IAK patients and has now passed the 1 year primary endpoint. Since the proposed cohort to be treated with AAT is otherwise similar in terms of recipient selection, islet manufacturing, medical management and post transplant follow-up, we will have a large carefully studies control cohort that will maximize trial efficiency and power to detect meaningful increases in islet mass manifest by single donor insulin independence rates at day 75. Since the day 75 single donor insulin independence rate in CIT-06 was relatively low (and nearly identical to the IAK experience in the CITR registry) at 17%, meaningful increases in engrafted mass gained by AAT therapy should be readily detectable in our study.

Use of an auxiliary islet graft in the subcutaneous tissue to monitor islet histopathology

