3. SELECTION AND WITHDRAWAL OF SUBJECTS

3.1 Inclusion Criteria

Subjects who meet *all* of the following criteria are eligible:

1. Male and female subjects age 18 to 70 years.
2. Subjects who are able to provide written informed consent and to comply with the procedures of the study protocol.
3. Subjects in the United States must have one of the following payment mechanisms in place:
 - a. Medicare,
 - b. A third-party insurer who agrees, via pre-authorization, to pay for participation in the study, or
 - c. Another mechanism of payment (self-pay, hospital, university, donations, etc.) for participation in the study.
4. Clinical history compatible with T1D with disease onset < 40 years of age and insulin-dependence for ≥ 5 years at the time of enrollment.
5. Absent stimulated c-peptide (< 0.3 ng/mL) in response to a MMTT [Boost[®] 6 mL/kg body weight (BW) to a maximum of 360 mL; another product with equivalent caloric and nutrient content may be substituted for Boost[®]] measured at 60 and 90 min after start of consumption.
6. Subjects who are ≥ 3 months post-renal transplant who are taking appropriate calcineurin inhibitor (CNI) based maintenance immunosuppression ([tacrolimus alone or in conjunction with sirolimus, mycophenolate mofetil, myfortic, or azathioprine; or cyclosporine in conjunction with sirolimus, mycophenolate mofetil, or myfortic] \pm Prednisone ≤ 10 mg/day).
7. Stable renal function as defined by a creatinine of no more than one third greater than the average creatinine determination performed in the 3 previous months prior to islet transplantation, until rejection, obstruction or infection is ruled out.
8. Subjects who meet one of the options in the following criterion are eligible for transplantation:
 - Reduced awareness of hypoglycemia manifested by a Clarke score of 4 or more measured upon study enrollment and at least one episode of severe hypoglycemia in the 12 months prior to study enrollment.

OR

 - a subject must have a reduced awareness of hypoglycemia manifested by a Clarke score of 4 or more and at least 1 episode of severe hypoglycemia;

OR

 - Any subject not meeting the hypoglycemia option must have an HbA1c $\geq 7.5\%$.

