7.8 Study Treatment Assignment Procedures

7.8.1 Blinding and Randomization

This is an open-label, non-randomized study. Therefore, no blinded treatment codes are required for the assignment of study treatment.

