Most of the secondary endpoints are measured before transplant, at day 75 (A1c, MMT, FSIGT, MAGE, c-peptide and Beta score) and at one year post-initial transplant (HbA1c, fasting and 90 minute MMTT, c-peptide, glucose, and c-peptide glucose creatinine ratio, MAGE, HYPO, Clarke survey, and Beta score). We will compare these markers with those in the CIT-06 controls using student's t-test, nonparametric test (e.g., Mann-Whitney U test, Wilcoxon signed rank test), or chi-square test when appropriate. A pre-post analysis will be used for these variables. For continuous variables that are normally distributed or that can be transformed to a normal distribution, we will compute an appropriate estimate and 95% confidence interval for the mean change and a paired t-test for testing that the mean change is zero. If an appropriate normalizing transform cannot be identified then a signed-rank test will be used to test for a significant change. Similarly, a McNemar test will be used to test for a significant change for dichotomous outcome variables.

For those continuous secondary endpoints that are only observable after transplantation or for whom

change from baseline are not meaningful we will compute estimates of the mean and 95% confidence intervals. Similarly, for binary endpoints we will compute the observed rates and exact 95% confidence intervals. Levels of these markers will be compared with those in the CIT-06 controls using student's t-test or nonparametric test (e.g., Mann-Whitney U test) when appropriate.

Regression models for continuous longitudinal data (mixed models) will be used to describe the profiles of change over time for each of the response variables where measurements are repeated over time. Similar models will be used to model dichotomous variables over time.

Survival analysis models will be used to compare time to becoming insulin dependent and to identify risk factors through Kaplan-Meier estimates and Cox regression models.

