10.3 Sample Size and Power Calculations

10.3.1 Power for Primary Endpoint

The primary end-point is the rate of insulin independence 75 days after the first single donor islet infusion. Our hypothesis is that the greater engrafted mass achieved with AAT will result in a significant increase in the proportion of subjects achieving insulin independence after the first dose. In the Edmonton era, single donor insulin independence occurred in less than 10% of patients. It appears that this is increased in patients treated with T cell depletion and Etanercept to 18%. In the CIT06 study patient who received islet transplantation after kidney grafting showed an insulin independence rate of 16.7%. A similar rate of insulin independence in IAK patients is seen in the CITR registry.

Table 7 gives the statistical power to reject the null hypothesis that the insulin independence rate is $\leq 16.7\%$, assuming a sample size of 20, using one-sided binomial test with 2.5% type 1 error. Sample size calculations assume asymptotic normality. We propose that AAT treatment will achieve single donor insulin independence in 50% of patients. With 20 patients we will have approximately an 87% power to reject the null hypothesis that the insulin independence rate is $\leq 16.7\%$ using a one-sided binomial test with 2.5% type 1 error. We believe the insulin independence rate after the first single donor islet infusion is at least as high as the control (reported in the CIT-06 study) using a one-sided test. If the true insulin independence rate is 55%, we would have 94% power to reject the null hypothesis. This suggests that we have a good chance of finding meaningful trends and potentially statistically significant differences between groups using highly relevant clinical end points in this pilot trial.

Table 7 Statistical Power to Reject the Null Hypothesis

True insulin independence rate in the study	Statistical power
45%	75%
50%	87%
55%	94%
60%	98%

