We have chosen to transplant 20 subjects. This will provide approximately 87% power to detect a difference of 50% insulin independence rate in islet transplanted subjects versus the estimated 16.7% insulin independence rate. Table 8 displays minimal detectable differences with 70%, 80% and 90% power. The smallest difference that can be detected with 90% power by a one-sided 2.5% level binomial test is 52% compared to 16.7%. The minimal detectable difference is 47% compared to 16.7% with 80% power. Using a one-sided test with 10% type 1 error rate, we could detect a medium effect of slightly more than 2 fold difference (38% vs. 16.7%) with 70% power.

Table 8 Minimum Detectable Difference for Insulin Independence Rate

Power	Minimum detectable difference
70%	43% vs. 16.7%
80%	47% vs. 16.7%

90%	52% vs. 16.7%
-----	---------------

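### The planned comparison of time to insulin dependence, read naturally, covers only recipients who first became independent, so it does not estimate the effect of AAT on durability

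*Combined protocol and SAP*

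**What the plan says.** The last paragraph of Section 10.1.2 says "Survival analysis models will be used to compare time to becoming insulin dependent", and adds a search for risk factors, using Kaplan-Meier estimates and Cox models. That is the whole specification. It gives no time origin, no risk set, no rule for recipients who never become independent, and nothing on repeat infusions or regained independence. Sections 5.8.3 and 6.1 mention an intent-to-treat analysis but do not tie it to this comparison.

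Four other parts of the plan bear on the meaning:

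- Inclusion criterion 4 (Section 3.1) requires "insulin-dependence for ≥ 5 years at the time of enrollment".
- The Study Definitions state: "Islet transplant recipients who do not meet the criteria for insulin independence will be considered insulin-dependent".
- Section 7.8.1 states: "This is an open-label, non-randomized study". The controls are the external CIT-06 cohort, which "has completed enrollment of 24 IAK patients" (Section 1.1).
- Section 4.1.2 names as key secondary endpoint the proportion of subjects insulin independent at 1 and 2 years after the first and last infusions.

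**The concern.** A subject who is insulin dependent at entry can become dependent again only after a spell of independence. If the survival curves start from that spell, the two groups are selected by their response to treatment. Section 2.1 hypothesises that AAT raises that response, so the AAT achievers would include people who would not have become independent without it. The control achievers would be a smaller and more selected group. The hazard ratio then mixes two things: what AAT does to durability, and the difference in who is being compared. Matching the cohorts at baseline does not remove the second, and it comes on top of a non-randomized comparison.

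Section 1.4 gives a reason to expect a difference in mix, since it suggests that a marginal islet mass may be lost over time through exhaustion. A reader of the report could take a flat or unfavourable curve as evidence on durability when it mainly reflects selection.

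**Working it through.** **Inputs from the plan.** Section 10.3.1 says CIT-06 patients "showed an insulin independence rate of 16.7"%; it also says "We propose that AAT treatment will achieve single donor insulin independence in 50% of patients" and "We have chosen to transplant 20 subjects". Section 1.1 gives 24 controls.

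**The plan's own figure.** The time-to-dependence analysis has no stated figure. The power statement that uses the same two rates does reproduce. With X ~ Binomial(20, 0.167), P(X ≥ 7) = 0.0375 and P(X ≥ 8) = 0.0114, so the one-sided 2.5% test needs 8 successes. Power at true rates of 45%, 50%, 55% and 60% is 74.8%, 86.8%, 94.2% and 97.9%, against 75%, 87%, 94% and 98% in Table 7.

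**Size of the achievers-only risk set.** Controls: 24 × 0.167 = 4.0. AAT: 20 × 0.50 = 10. These are single-infusion, day-75 rates; later infusions would enlarge both sets and change their make-up.

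**Information in that set.** Take all 14 as events (the best case), with control share q = 4/14. Then √(14 × 0.286 × 0.714) = 1.690.

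- Power for a hazard ratio of 0.5, two-sided 5%: Φ(0.693 × 1.690 − 1.96) = Φ(−0.79) = 21.5%.
- Hazard ratio needed for 80% power: exp(−(1.96 + 0.842)/1.690) = 0.19.

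**Illustration A, islet mass.** These are assumptions, not document figures. Mass M is normal with SD 1, independence starts at time zero, and the yearly hazard of losing it is 0.3 × exp(−0.7M). Controls have mean 0 and become independent if M > 0.967, which gives 16.7%. Two-year freedom among achievers is the mean of exp(−0.6 × exp(−0.7M)) over those above the threshold. The all-subject figure is that value times the proportion independent.

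| Setting | Independent | 2-year freedom, achievers only | 2-year independence, all subjects |
|---|---|---|---|
| Control | 16.7% | 80.4% | 0.167 × 0.804 = 13.4% |
| AAT adds 0.967 to everyone's mass, same threshold | 50% | 83.0% | 0.50 × 0.830 = 41.5% |
| AAT adds marginal responders (threshold lowered to 0, mass unchanged) | 50% | 69.6% | 0.50 × 0.696 = 34.8% |

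In the uniform-shift row the achievers-only gap is 83.0 − 80.4 = 2.6 points, and the all-subject gap is 41.5 − 13.4 = 28.1 points. Each person's hazard is multiplied by exp(−0.7 × 0.967) = 0.51, yet the achievers-only curves imply ln(0.830)/ln(0.804) = 0.85 at 2 years. In the marginal-responder row AAT leaves every person's hazard unchanged, yet the curves imply ln(0.696)/ln(0.804) = 1.66. Neither contrast recovers the effect on durability.

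**Illustration B, a different model.** These hazards are also assumed. Subjects who would be independent either way lose it at 0.30 per year on control. AAT multiplies that by 0.8, a true benefit. Subjects independent only because of AAT lose it k times as fast. One-year retention among achievers is exp(−0.30) = 74.1% on control and [0.167 × exp(−0.24) + 0.333 × exp(−0.24k)]/0.5 on AAT.

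| k | AAT achievers, 1 year | Apparent hazard ratio | All subjects, control vs AAT |
|---|---|---|---|
| 1 | 78.7% | 0.80 | 12.4% vs 39.3% |
| 1.5 | 72.7% | 1.06 | 12.4% vs 36.4% |
| 2 | 67.5% | 1.31 | 12.4% vs 33.7% |
| 3 | 58.7% | 1.78 | 12.4% vs 29.3% |

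In 2,000 simulated trials per setting (4 control achievers, 2-year follow-up), the Cox estimate pointed to harm in 41% at k = 1, which is chance alone, 60% at k = 2 and 74% at k = 3.

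**The case against.** **The plan does not say that only achievers are analysed.** This stands. Because the Study Definitions class every non-independent recipient as dependent, an analysis of all recipients with early failures would fit the text. But speaking of becoming dependent, in people who all enter dependent, most naturally means losing an independence once gained. Leaving the risk set open also lets it be chosen after the data are seen.

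**A reader might infer that the analysis will make AAT look harmful.** The documents do not support that. Section 2.1 hypothesises that AAT raises engrafted mass. With mass shifted uniformly, AAT stayed ahead among achievers in all 20 combinations of slope (0.3 to 2) and base hazard (0.1 to 1.0 per year) that were tried. With a narrower spread of mass on AAT (SD 0.6) the groups are about equal, 80.4% vs 80.0%. Reversal needs AAT-added responders to lose function faster, by an assumed factor for which the plan gives no figure. What remains is that the contrast is not interpretable in either direction.

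**Durability is already assessed without this selection.** This also stands, and it limits the impact. Section 10.1.2 treats the key secondary endpoint as the direct evidence of durability, Section 2.1 makes durability a secondary part of the primary objective, and no alpha, power or decision rule rests on the survival comparison. Section 10.1.2 also promises qualifiers on significant secondary findings.

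**The risk sets ignore repeat infusions.** Correct. Up to three are allowed (Section 4), so 4 and 10 are only the starting sizes.

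**Conclusion.** The concern holds in a limited form. On its natural reading, the survival comparison conditions on a post-treatment outcome that AAT is meant to change, in about 4 controls and 10 treated subjects before repeat infusions. It does not estimate the effect of AAT on durability. Depending on assumptions, it can hide most of the benefit (a 2.6-point gap against 28.1 points in all subjects) or point the wrong way (80% vs 70% among achievers, while all-subject independence is 13% vs 35%).

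The risk-set sizes follow from the plan's own rates. The hazards, the mass model and k are illustrative, so the percentages show what is possible and do not forecast this trial. Two stronger inferences should not be drawn: that reversal is expected, or that the trial's durability evidence is compromised. The unconditional proportions in Section 4.1.2 carry that evidence; this analysis supports them.

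**What to change.** Amend the survival paragraph of Section 10.1.2, or the SAP, as follows.

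- Make the between-group comparison in all transplanted subjects, with time zero at the first infusion.
- Use a measure that needs no selection: the probability of being insulin independent over time, or restricted mean insulin-free time to 2 years. Never-independent subjects contribute zero. Independence gained after a second or third infusion counts from when it is gained. Simply calling never-independent subjects failures at time zero would leave those later gains without a rule.
- State how the dates of gaining and losing independence are set from the visit data, and how regained independence is counted.
- Optionally add time to islet graft failure (c-peptide < 0.3 ng/mL, as in the Study Definitions) as a separate outcome. It is not a substitute, because partial function counts as success there.
- Label any curve or Cox model restricted to achievers descriptive, and report the number at risk in each group.

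The cost is a few sentences of SAP wording. The new measures use the independence determinations that the planned analysis already needs in both cohorts, so no new data are required.

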10.1.3 Exploratory Endpoints

Exploring novel approaches to monitoring islet graft injury will serve as the basis for hypotheses generation in future trials. We will calculate descriptive statistics for the safety and efficacy of the new approaches. Adverse events rates will be tabulated and 95% confidence intervals (CI) will be calculated. We will calculate the mean, median, minimum, maximum, inter-quartile ranges, and 95% CI of loss of engrafted islets estimated by early post infusion release of insulin specific DNA, TAT and C3a. Success rate and 95% CI will be estimated.

Other secondary and exploratory endpoints include relative functional engrafted islet mass, the proportion achieving insulin independence, the proportion achieving HbA1c \leq 6.5% and an absence of severe hypoglycemic events, the proportion achieving HbA1c $<$ 7.0%, reduction in HbA1c of at least 1 point, the change in Clarke score, c-peptide, Glycemic lability index (LI), glucose and glucose variability. These endpoints will also be analyzed using descriptive statistics.

10.2 Subject and Demographic Data

10.2.1 Baseline Characteristics and Demographics

Summary descriptive statistics for baseline and demographic characteristics will be provided for all enrolled subjects. Demographic data will include age, race, sex, BW, and height; these data will be presented in the following manner:

- a. Continuous data (*i.e.*, age, BW, and height) will be summarized descriptively by mean, standard deviation, median, range, and 95% confidence interval.
- b. Categorical data (*i.e.*, sex and race) will be presented as enumerations and percentages.

10.2.2 Medical History

Medical history will be collected, including the existence of current signs and symptoms and clinical significance for each body system.

10.2.3 Use of Medications

All medications used will be coded using the MedDRA drug dictionary. The number and percentage of subjects receiving concomitant medications or therapies will be presented. Statistical presentation of concomitant medications or therapies may be further summarized by relevant groups such as gender, age, race, etc.

10.2.4 Changes in Renal Function

Statistical presentation of changes in renal function over time will be further defined in the SAP.

10.2.5 Study Completion

The percent of subjects who complete the study, losses to follow-up, times to lost to follow-up, and reasons for discontinuation (e.g., AEs) will be presented.

